Despite worrying post marketing case reports of serious psychiatric adverse events with varenicline, evidence for safety of varenicline in treated outpatients with schizophrenia, bipolar disorder, and major depressive disorder from placebo controlled RCT's and case controlled trials is mounting rapidly.^{60,63,67,85,269-271} There have been reports of depressed mood, agitation, behavioral disturbance, suicidal ideation, worsening of psychotic symptoms and suicide in people attempting to quit smoking with varenicline. The role of varenicline in these symptoms from uncontrolled case reports is not known, and, while the FDA is investigating these reports and has ordered further study of varenicline in smokers with psychiatric illness, as yet, no information is available on rate of occurrence or likely association with varenicline. Because of reporting bias, confounding, uncertain denominator, causality and even adverse event rates are impossible to infer from such reports. The underlying disease of nicotine dependence or process of smoking cessation could be the causal factor. Controlled trials are needed to establish causality, and all controlled trials to date support the safety of varenicline in those with psychiatric illness. No large controlled trial has shown a signal for varenicline to increase psychiatric adverse events over placebo or other active treatment (NRT or bupropion). Psychiatric adverse events have not been associated with varenicline treatment in placebo controlled clinical trials involving over 8,000 individuals or in case controlled trials in over 117,000 individuals.^{62,63,270,272} Varenicline has also not been associated with an increased incidence of adverse psychiatric events in prospective^{59,61,273} or placebo controlled trials in people with psychiatric illness²⁷⁴ such as schizophrenia,^{30,60,67,85,271,275} bipolar disorder,²⁶⁸ or depression.^{272,276,277}

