Data and safety monitoring plan: Protection of research participants begins with the eligibility criteria, which are designed to exclude individuals with serious medical conditions that would preclude their ability to safely participate in the intervention. During the study, clinical care will be provided by the participants' usual specialty mental health providers and the primary care physician, with communication with the study staff. Participants will be made aware of this delineation of responsibility. The exception to this is participants whose primary psychiatrist is the study psychiatrist. Participants in the active intervention will be monitored for psychiatric symptoms by the health coach. Recognizing the opportunity for early detection of clinical problems and the small risk of study-related morbidity, we will perform periodic safety assessments for intervention and control participants. We will inquire about cardiovascular, musculoskeletal, psychiatric and possible medication-related symptoms at 6-month intervals. We will identically apply a process to each randomized group and collect self-reported symptoms, health care utilization and records related to CVD and mental health outcomes, including emergency department use and hospitalizations, and ask standard questions regarding possible medication side effects. Clinically significant results will lead to referral to the primary care physician and/or psychiatrist. Information that comes to the attention of study personnel informally (e.g., through data collection or intervention activities at the center) may also lead to referral. Symptoms that will lead to referral include (but are not limited to) those that suggest cardiovascular disease (e.g., exertional chest pain, dyspnea, presyncope or syncope), uncontrolled hypertension, uncontrolled diabetes, complications of physical activity or psychiatric symptom exacerbation. Participants are also queried at these same time points about possible adverse events (defined below). Positive responses trigger an adverse event (AE) record, which is reviewed and classified as gastrointestinal, cardiovascular, musculoskeletal, psychiatric, or other in nature. This information is then reported to the DSMB. Similar information reported by participants at other times (e.g., during intervention classes) is noted and followed up with as needed to assure participant safety. The following constitute adverse events (AEs): heart attack, stroke, transient ischemic attack, heart failure, coronary angioplasty or bypass surgery, angina pectoris, broken bone, torn ligament, any other serious injury to the bone or muscle, seizure or hospitalization for suicidal or homicidal ideation. Evidence of the occurrence of these events is based on participant self-report that a health care professional has diagnosed the condition. We will attempt to verify the diagnosis through contact with the physician. Though not considered AEs for this study, we also will track and report the incidence of hyperlipidemia, gallbladder disease, diabetes, cancer, emergency department use and hospitalization. All other outcomes that may be construed as being an adverse consequence of study participation, such as an injury while performing a study measurement, are documented, reviewed, and followed up on as needed by a study clinician.

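### The adverse-event list omits death, suicide attempt, psychiatric admission other than for suicidal or homicidal ideation, and the common drug side effects; the plan's other safety routes recover only part of this

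*Combined protocol and SAP*

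**What the plan says.** Section 17 (data and safety monitoring plan) has participants in both arms asked at scheduled times about adverse events. A positive answer opens an AE record, which goes to the DSMB after being "reviewed and classified as gastrointestinal, cardiovascular, musculoskeletal, psychiatric, or other in nature". The definition is an enumeration. It opens "The following constitute adverse events (AEs): heart attack, stroke, transient ischemic attack, heart failure, coronary angioplasty or bypass surgery", goes on through angina, fracture and ligament injury, and closes with "any other serious injury to the bone or muscle, seizure or hospitalization for suicidal or homicidal ideation".

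A second group of events is followed but kept outside the definition: "Though not considered AEs for this study, we also will track and report the incidence of hyperlipidemia", together with gallbladder disease, diabetes, cancer, emergency department use and hospitalisation.

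On evidence, "Evidence of the occurrence of these events is based on participant self-report that a health care professional has diagnosed the condition". The next sentence adds: "We will attempt to verify the diagnosis through contact with the physician".

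Elsewhere:
- Section 7 (event surveillance) collects health care use, records on cardiovascular and mental health outcomes, and SAFTEE side-effect data by the same process in both arms.
- Section 13 compares emergency visits, hospitalisations and BPRS between arms.
- Section 15 provides for questionnaire surveillance of serious adverse events and a safety officer who reviews and reports them.
- Section 16 lists nausea, insomnia and abnormal dreams as adverse events of the study drugs. On varenicline it says: "There have been reports of depressed mood, agitation, behavioral disturbance, suicidal ideation, worsening of psychotic symptoms and suicide in people".

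**The concern.** Active participants may take varenicline, or bupropion with nicotine replacement, for up to 18 months, in a population with serious mental illness. The plan's own risk section identifies psychiatric deterioration and suicide as the events that raised alarm about varenicline. Yet the list that governs AE records has one psychiatric entry, tied to admission for ideation. A table built from it could show similar AE counts in the two arms while deaths, suicide attempts and admissions for psychosis, mania or depression lay outside it. The DSMB would have no assured by-arm count of those events.

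**Working it through.** No figure in the plan needs reproducing. The check compares the list with the risks the protocol names and with the other collection routes.

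**Step 1: the list against its own classes.** Counting angioplasty or bypass as one entry, there are 11 entries:
- Cardiovascular, 6: heart attack, stroke, transient ischaemic attack, heart failure, revascularisation, angina.
- Musculoskeletal, 3: fracture, ligament tear, other serious bone or muscle injury.
- Psychiatric, 1: admission for suicidal or homicidal ideation.
- Other, 1: seizure.
- Gastrointestinal, 0.

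6 + 3 + 1 + 1 + 0 = 11. The gastrointestinal class has nothing to hold. The one digestive condition mentioned nearby, gallbladder disease, is in the group declared not to be AEs.

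**Step 2: the list against the varenicline reports in Section 16.** Six problems are named: depressed mood, agitation, behavioural disturbance, suicidal ideation, psychotic worsening and suicide. One of the six (ideation) can meet the definition, and only through an admission.

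**Step 3: the list against the other routes.**

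| Event | On the AE list? | Other route | What remains open |
|---|---|---|---|
| Death, any cause | No | Undefined SAE route; catch-all | Not named in any monitoring or analysis text |
| Suicide attempt | No | Emergency visit or admission, if one results; undefined SAE route; catch-all | Not named; an attempt without hospital contact has no assured place |
| Admission for psychosis, mania or depression | No | All-cause hospitalisation, compared by arm in Section 13 | No stated split by cause |
| Nausea, insomnia, abnormal dreams | No, though Section 16 calls them adverse events | SAFTEE, both arms | No analysis in Section 13; no stated route to the DSMB |
| Psychiatric worsening without admission | No | BPRS, compared by arm | Collected at baseline, 6 and 18 months only (Table 2); a difference in means does not count individual relapses |
| Seizure | Yes | – | – |

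**Step 4: what starts a record.** The scheduled trigger is the participant's own answer. Physician contact comes after it, so it can confirm a reported event but cannot find one that nobody reported. A participant who has died cannot answer. Section 13 treats those with missing smoking data as smokers and has no separate rule for deaths, so the efficacy data would not show a death as such either.

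**Step 5: equal detection.** The health coach screens for suicidality weekly at first and then at least twice a month (Section 17, minimising drug risks). Only the active arm has a coach, so events learned between visits are more likely to surface there.

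**The case against.** The plan does far more safety collection than the list suggests, and most of that case stands. All-cause hospitalisation and emergency use are secondary outcomes with a specified between-arm model, and Section 17 undertakes to report them: "we also will track and report the incidence of hyperlipidemia, gallbladder disease, diabetes, cancer, emergency department use and hospitalization". A psychotic relapse that leads to admission is therefore counted. BPRS is compared by arm, SAFTEE is applied identically to both arms, and records supplement self-report. Section 7 (RE-AIM) commits to reporting all outcomes, including potential adverse events. The safety officer handles serious adverse events, a catch-all covers outcomes construed as consequences of participation, and adverse events go to the IRB, the DSMB and the NIH under those bodies' own policies.

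Three stronger readings are tempting, and the documents do not support them:
- **That every drug side effect is left out.** Seizure is listed, and Section 16 calls it bupropion's most serious adverse effect.
- **That the safety comparison as a whole would miss the named risks, or that any death is certain to go uncounted.** The routes above recover part of them, and a fatal heart attack is at least a listed type of event.
- **That the nausea rate measures the loss.** At 30% or more of users and 220 / 2 = 110 per arm, 0.30 × 110 = 33 participants if all took varenicline, or 0.30 × 55 = 16.5, about 17, if half did. The documents give no uptake figure, bupropion is an alternative, and SAFTEE would ask about these side effects.

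The routes still do not close the gap. The catch-all depends on a judgement of causality, and its stated outcome is documentation and follow-up, not DSMB reporting. The SAE route has no definition to work from. It can also be argued that the gastrointestinal class and Section 16's wording show AE records are meant to be wider than the list. If so, the passages contradict each other and need reconciling all the same.

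**Conclusion.** The point holds as a stated rule that gives an incomplete AE count. It is not a failure to collect safety data. The list omits death from any cause, suicide attempt, psychiatric admission other than for suicidal or homicidal ideation, and the common side effects that Section 16 calls adverse events. It conflicts with its own gastrointestinal class, and Section 15 relies on a serious-adverse-event category that is never defined. After allowing for the other routes, three gaps remain: admissions are not split by cause, AEs and SAFTEE have no by-arm analysis, and death and suicide attempt are named nowhere in the monitoring or analysis text.

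The size is one of content (one of six named psychiatric problems, on admission only). The number of participants affected cannot be derived from the documents. The conclusion assumes the list is exhaustive, as its wording as a definition implies. The reporting policies of the IRB, DSMB and NIH are not in the documents and may require deaths to be reported regardless. This should be changed, but it does not undermine the primary comparison.

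**What to change.** Reconcile Section 7 (event surveillance), Section 15 (safety monitoring), Section 16 (summary of risks) and Section 17 (monitoring plan):

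1. Define AE and SAE to include death from any cause, suicide attempt or self-harm, any psychiatric hospitalisation, and clinically significant side effects found on SAFTEE.
2. Accept the health care and programme records already collected in both arms as evidence, as well as self-report, so that an event can be entered without the participant's own account.
3. Report AEs, SAEs and SAFTEE items by arm, to the DSMB and in the results, from the scheduled visits common to both arms. Say which visits count: Table 2 includes month 15, whereas Section 17 speaks of six-monthly enquiry.
4. List events learned between visits separately, including those from coach screening, which exists only in the active arm.

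The cost is protocol wording, a revised AE form and more AE records to review. Most of the inputs are already planned. The records in Section 7 are limited to cardiovascular and mental health outcomes, so deaths from other causes would need a vital-status item, which could draw on the programme and clinic information described in Section 6. Where visits are already complete, much could still be classified from the records held, before the arms are compared.

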18. SUBSTUDY OF FACTORS RELATED TO INTERVENTION IMPLEMENTATION

Semi-structured interviews with selected staff

Human subjects involvement and characteristics: To better understand the intervention implementation process and the perspectives of community mental health program leadership and staff, psychiatrists and health coaches at Bayview and Family Services Agency, Inc. and about potential barriers and facilitators of the intervention, perceived effectiveness and plans for sustainability, we will conduct a series of semi-structured interviews. We will conduct interviews at baseline, and then follow-up interviews at the end of study. We expect to conduct interviews with up to 50 people, or a total of 100 interviews.

Sources of materials. The interviews will inquire about perceived effectiveness, ease of or barriers for the intervention, fit within the organization and financial models for continued support. They will be conducted in a private office will be approximately 30 minutes in length and will be audio recorded. Recordings will be transcribed.

Potential risks. Risk of loss of confidentiality is the main study risk. We expect this risk to be very low.

Protocol: Trial of Integrated Smoking Cessation, Exercise and Weight Management in SMI

Plans to minimize this risk are described below.

Adequacy of protection against risks

1. Recruitment and informed consent. Procedures for recruitment, consent, and data collection will be reviewed and approved by the Johns Hopkins Institutional Review Boards and Sheppard Pratt Institutional Review Boards. We will invite individuals to participate in interviews in person and/or by letter/email, and we will obtain written informed consent for these interviews. We will plan to interview the health coaches, exercise leaders, Family Services Agency and Bayview Psychiatry leadership, study clinicians, and psychiatrists and psychiatric nurse practitioners at the sites. We also aim to interview a purposeful sample of other mental health program staff reflecting a range of responsibilities (e.g., therapist, case manager, rehabilitation program counselors). We anticipate 60% women and 25% African-American in this sample, similar to current employee demographics.

2. Protection against risk:

Breach of confidentiality: All information will be considered confidential. This confidentiality will be assured through several mechanisms. Transcripts of interviews will have names removed. The tapes will be kept for 7 years and then destroyed. Finally, neither the mental health program nor staff will be identified by name in any publications. Employees will be assured that their participation in the study and information shared in the interviews will not affect their employment or their evaluation.

Participant reimbursement. We plan to give a \$50 gift card for each interview.

Potential benefits of the proposed research to the subjects and others: There are no direct individual benefits. Potential benefits to others include the possibility that the research will lead to the understanding of factors that may be important for sustaining and disseminating smoking cessation interventions for persons with serious mental illness in community mental health organizations.

Importance of knowledge to be gained: Persons with serious mental illness have 2-5 times the smoking prevalence, and higher overweight/obesity and physical inactivity than the general population and consequently a high burden of CVD and early death. It is critical to know if interventions to improve their health can be sustained and what factors predict sustainability so that interventions can be translated and optimally spread into the community. The goal of this study is to collect information from staff to understand factors related to sustainability and dissemination. The minimal risks are offset by the potential benefits to populations with chronic mental illness who would benefit from future interventions.

Data and safety monitoring plan: This is an observational study. No interventions are planned. [name] will have responsibility for monitoring and oversight of any problems/events for this research.

Surveys with program staff

Human subjects involvement and characteristics: To study factors influencing intervention implementation and possible future dissemination, we will invite all mental health program staff to participate in a survey. These surveys will complement and add to the information we collect from the smaller number of semi-structured interviews (described above), will contain some standard implementation science measures, and will reach a wider range of staff. We aim to invite staff in Bayview Adult Psychiatry programs and Family Services Agency, Inc in the psychiatric day program and clinic to participate.

Sources of materials. The surveys will be available through Qualtrics, or if preferred, on paper. The questions will ask about implementation climate, attitudes towards evidence-based practices, perceptions of the role of mental health and medical health care sectors in addressing clients' somatic health needs; perceptions of the intervention, and potential stigma towards persons with SMI.

Potential risks. Risk of loss of confidentiality is the main study risk. We expect this risk to be very low. Plans to minimize this risk are described below.

Adequacy of protection against risks

1. Recruitment and informed consent. Procedures for recruitment and data collection will be reviewed and approved by the Johns Hopkins Institutional Review Boards and Sheppard Pratt Institutional Review Boards. We will invite individuals to participate in surveys in person and/or by letter/email. We aim to invite staff in Bayview Adult Psychiatry programs and Family Services Agency, Inc in the psychiatric day program and clinic to participate. Individuals could participate in the survey and the interview.

Protocol: Trial of Integrated Smoking Cessation, Exercise and Weight Management in SMI

2. Protection against risk:

Breach of confidentiality: All information will be considered confidential. This confidentiality will be assured through several mechanisms. The surveys will not contain names or other identifying information. The mental health program and staff will be identified by name in any publications. Employees will be assured that their participation in the study and information shared in the survey will not affect their employment or their evaluation.

Participant reimbursement: We plan to give a \$25 gift card for each survey.

Potential benefits of the proposed research to the subjects and others: There are no direct individual benefits. Potential benefits to others include the possibility that the research will lead to the understanding of factors that may be important for sustaining and disseminating smoking cessation interventions for persons with serious mental illness in community mental health organizations.

Importance of knowledge to be gained: Persons with serious mental illness have 2-5 times the smoking prevalence, and higher overweight/obesity and physical inactivity than the general population and consequently a high burden of CVD and early death. It is critical to know if interventions to improve their health can be sustained and what factors predict sustainability so that interventions can be translated and optimally spread into the community. The goal of this study is to collect information from staff to understand factors related to sustainability and dissemination. The minimal risks are offset by the potential benefits to populations with chronic mental illness who would benefit from future interventions.

Data and safety monitoring plan: This is an observational study. No interventions are planned. [name] will have responsibility for monitoring and oversight of any problems/events for this research.

